#### **6.5. Long-term Follow-up for Safety**

SAEs will be reported through 30 days after the last dose of SRF617, 30 days after the last dose of etrumadenant, or 90 days after the last dose of zimberelimab (30 days after the last dose of zimberelimab if the patient initiates new anticancer therapy), whichever is later. Pregnancy events in female partners of male trial participants will be followed for 30 days after the last dose of SRF617, 30 days after the last dose of etrumadenant, or 90 days after the last dose of zimberelimab, whichever is later. Long-term follow-up reporting may be conducted in person or by phone.

#### **6.6. Concomitant Medications or Procedures**

##### **6.6.1. Transfusion Support (Prophylaxis or Supportive Care)**

Blood cell transfusion (packed RBCs or platelets) are permitted as clinically indicated. Transfusions are also permitted to meet hemoglobin and platelet inclusion criteria. However, the patient must have a stable hemoglobin level and platelet count for  $\geq 2$  weeks prior to dosing without transfusion.

##### **6.6.2. Prohibited Medications**

During the study treatment period, the following medications are prohibited:

- Any additional anticancer therapy.
- Other investigational agents.
- Systemic immunostimulatory agents (including but not limited to IFNs and IL-2).
- Systemic immunosuppressive medications (eg, cyclophosphamide, azathioprine, methotrexate, thalidomide, and antitumor necrosis factor- $\alpha$  agents), including

systemic corticosteroids administered at > 10 mg/day prednisone or equivalent on a long-term basis are prohibited.

- Acute, low dose ( $\leq$  10 mg/day prednisone or equivalent) systemic immunosuppressant medications for management of adverse events or premedication are allowed after Medical Monitor approval has been obtained.
- Inhaled steroids for the management of asthma/chronic obstructive pulmonary disease are permitted.
- If there is a clinical indication for any medication or vaccination specifically prohibited during the trial, discontinuation from trial therapy may be required. The Investigator should discuss any questions regarding this with the Medical Monitor.
  - Exception: The Sponsor is supportive of patients receiving a Health Authority approved COVID-19 vaccine if they have no known contraindications to the vaccination. If administered, the name of the vaccine, the dose, and the dates administered should be documented in the medical records as well as the concomitant medication section of the eCRF. Investigators should have an informed risk/benefit discussion with the patient in making the decision to receive the vaccine and monitor for toxicity as there could be unknown risks of (1) heightened immune response and thus toxicity or (2) diminished immune response to either the study treatment, the vaccine, or both. If a trial patient decides to pursue an approved COVID-19 vaccination, the Sponsor recommends scheduling vaccination such that the full vaccination course occurs at least 2 weeks before C1D1, when possible.
- Given potential interactions with etrumadenant, co-administration of the following medications are prohibited:
  - BCRP substrates with a narrow therapeutic window, administered orally (eg, prazosin, rosuvastatin).
  - P-gp substrates with a narrow therapeutic window, administered orally (eg, digoxin).
  - Strong CYP3A4 inducers (eg, rifampin, phenytoin, carbamazepine, phenobarbital, and St. John's Wort) and strong CYP3A4 inhibitors (eg, clarithromycin, grapefruit juice, itraconazole, ketoconazole, posaconazole, telithromycin, and voriconazole).
  - Refer to [Appendix 1](#) and the following for more examples of relevant substrates, inhibitors, and inducers with the potential for drug-drug interactions with etrumadenant: <https://www.fda.gov/drugs/drug-interactions-labeling/drug-development-and-drug-interactions-table-substrates-inhibitors-and-inducers>.

### 6.6.3. Other Concomitant Therapies or Procedures

- Radiation therapy to a symptomatic or progressing solitary lesion including the brain may be allowed at the Sponsor's discretion and if the Investigator feels the patient is deriving clinical benefit/disease control in the other disease sites.

- Any other medication that is considered necessary for the patient's welfare, including antimicrobial prophylaxis and growth factor support, and that is not expected to interfere with the evaluation of study drug may be given at the discretion of the Investigator.
- Supportive care medicines (eg, bisphosphonates or RANK ligand inhibitors) are allowed on trial.
- Patients may receive a COVID-19 vaccination. Because COVID-19 vaccines are reported to have side effects similar to those of an infusion reaction, the vaccination should take place at a different place and time from any trial infusion. For vaccines requiring 2 doses, both doses should be administered in this fashion. For any patient presenting to clinic or emergency department with symptoms consistent with COVID-19 infection, testing for the presence of the novel coronavirus is recommended, as well as isolation and quarantine following institutional and local health authority guidance (for experience and recommendations specific to oncology clinics). AEs or treatment discontinuation suspected to be attributable to infection with COVID-19 should be indicated as such on the relevant case report forms.

#### 6.6.4. Contraception and Pregnancy

The effects of the study treatment on conception, pregnancy, and lactation are unknown.

Male patients with female partners of reproductive potential are required to use highly effective contraceptive measures from the first dose of study treatment until 30 days after the last dose of SRF617, 30 days after the last dose of etrumadenant, or 90 days after the last dose of zimberelimab, whichever is later.

- A man is considered fertile after puberty unless permanently sterile by bilateral orchiectomy.
- A female partner of a male patient is considered fertile following menarche and until becoming post-menopausal unless permanently sterile.
  - Permanent sterilization methods include hysterectomy, bilateral salpingectomy, and bilateral oophorectomy.
  - A postmenopausal state is defined as no menses for 12 months without an alternative medical cause. A high follicle-stimulating hormone (FSH) level in the postmenopausal range may be used to confirm a post-menopausal state in women not using hormonal contraception or hormonal replacement therapy. However, in the absence of 12 months of amenorrhea, a single FSH measurement is insufficient.

Highly effective contraception is defined as use of one or more methods that result in a low failure rate (ie, < 1%). Highly effective contraceptive measures include:

- Combined (estrogen- and progestogen-containing) hormonal contraception associated with inhibition of ovulation: oral, intravaginal, transdermal
- Progestogen-only hormonal contraception associated with inhibition of ovulation: oral, injectable, implantable

- Intrauterine device
- Intrauterine hormone-releasing system in combination with a barrier method (preferably male condom)
- Surgical sterilization
  - Male patient is vasectomized (with documented medical confirmation of surgical success) and is the sole sexual partner of a female with reproductive potential
  - Female partner of the male patient has undergone bilateral tubal ligation
- Complete sexual abstinence defined as refraining from heterosexual intercourse during the entire period of risk associated with study treatment. The reliability of sexual abstinence needs to be evaluated in relation to the duration of the clinical trial and the preferred and usual lifestyle of the patient

To ensure proper birth control, male patients, when having sexual intercourse with a female of reproductive potential, should use an efficient barrier contraceptive (condom plus spermicide); the respective partner should also use an additional efficient contraceptive method (eg, oral pills, intrauterine device, or diaphragm, and spermicide).

Patients should not donate sperm for 4 months after the last dose of any study drug.

## **7. STUDY DRUG MATERIALS AND MANAGEMENT**

On visit days where study drug is administered in the clinic, dosing will be performed in a monitored setting in which there is immediate access to trained personnel and adequate equipment and medicine to manage potentially serious reactions.

### **7.1. SRF617**

#### **7.1.1. Description of SRF617**

SRF617 drug product is a sterile filtered liquid, aseptically filled into a single-use stoppered glass vial and sealed with a flip-off seal. SRF617 drug product contains at least 2.0 mL at a target concentration of 50 mg/mL in 10 mM histidine, 280 nM sucrose, and 0.02% polysorbate 20, pH 6.0. All lots of drug product are tested to ensure product identity, strength, quality, purity, and potency. For IV infusion, the drug product will be diluted into normal saline (0.9%, Sodium Chloride Injection, US Pharmacopeia) for injection as diluent. Additional details on the preparation and administration of SRF617 drug product will be provided to the Investigator in the Pharmacy Manual.

#### **7.1.2. SRF617 Dosage**

Patients will receive SRF617 1400 mg IV q2 weeks on Days 1 and 15 of a 28-day cycle. SRF617 is administered as an IV infusion supplied by the Sponsor.

Dose reductions and discontinuations for SRF617 in individual patients may be made based on the clinical judgment of the Investigator with notification to the Medical Monitor/Sponsor (see Section [7.4](#)).

#### **7.1.3. SRF617 Administration**

SRF617 will be administered as an IV infusion. SRF617 infusion should be administered under the supervision of a physician, or other trial personnel, experienced in the use of IV agents. The suggested infusion duration range is approximately 30 to 60 minutes. The timing of SRF617 administration relative to etrumadenant and zimberelimab is shown in [Table 5](#).

**Table 5: Timing of Administration of Study Drug on Infusion Days in Trial SRF617-201**

| Cycle/Day                         | Order/Timing of study drug administration a   |
|-----------------------------------|--|
| Day 1 of each cycle b  | 

SRF617 will be administered first

Etrumadenant will be taken orally after at least a 30-minute observation period that begins at the end of the SRF617 infusion

Zimberelimab will be administered at least 30 minutes after the patient has taken etrumadenant

 |
| Day 15 of each cycle b | 

SRF617 will be administered first

Etrumadenant will be taken orally after at least a 30-minute observation period that begins at the end of the SRF617 infusion

  |

a The timing and order of administration of study drug may be changed at the direction of the trial Safety Review Committee.

b On Day 1 and Day 15 infusion visits, patients will hold etrumadenant administration until directed by trial personnel.

Missed doses of SRF617 or zimberelimab (more than  $\pm$  3 days) should not be made up; rather, follow the schedule for the next biweekly dose. There should be a minimum of 11 days between SRF617 infusions and between zimberelimab infusions. The  $\pm$  3-day window may be used one time per patient during the study treatment period without contacting the Sponsor. Please contact the Sponsor if a second  $\pm$  3-day window is needed.

Please refer to the Pharmacy Manual for detailed administration instructions.

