## **7.3. Zimberelimab**

### **7.3.1. Zimberelimab Dosage**

Patients will receive zimberelimab 480 mg IV q4 weeks on Day 1 of a 28-day cycle. Zimberelimab is administered as an IV infusion supplied by the Sponsor.

There will be no dose modifications for zimberelimab in this trial. See [Table 9](#) for additional information about management of drug-related toxicities with zimberelimab.

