2.2 Study Treatment

Treatment cycles are 28 days in duration.

Study Drug	Dosing Route and Schedule	Initial Dose	1st Reduction	2nd Reduction
SRF617	iv q2w on Days 1 and 15 of each cycle	1400 mg	700 mg	350 mg
Etrumadenant	orally at a daily dose	150 mg	100 mg	75 mg
Zimberelimab	iv q4w on Day 1 of each cycle	480 mg	NA	NA

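### The protocol's missed-dose paragraph applies SRF617's two-weekly wording to zimberelimab, so the four-weekly antibody has no clear missed-dose or spacing rule of its own

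*Protocol*

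**What the plan says.** The missed-dose instruction sits in Protocol Section 7.1.3 (SRF617 Administration), directly under Table 5. It names both antibodies, "Missed doses of SRF617 or zimberelimab (more than" three days either way), and says that such doses "should not be made up; rather, follow the schedule for the next biweekly dose". It then sets one floor for both drugs: "There should be a minimum of 11 days between SRF617 infusions and between zimberelimab infusions". It adds that the "3-day window may be used one time per patient during the study treatment period without contacting the Sponsor".

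The two antibodies have different schedules. For SRF617, Section 7.1.2 says: "Patients will receive SRF617 1400 mg IV q2 weeks on Days 1 and 15 of a 28-day cycle". For zimberelimab, Section 7.3.1 says: "Patients will receive zimberelimab 480 mg IV q4 weeks on Day 1 of a 28-day cycle". The Synopsis dosing table, Section 4.4, and Table 2 with its footnote n agree with Section 7.3.1. SAP Section 2.2 has "iv q4w on Day 1 of each cycle", and SAP Section 8.1 plans 480 mg of zimberelimab per cycle, which is one infusion. In Table 5 the Day 15 row lists only SRF617 and etrumadenant.

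**The concern.** For SRF617 the paragraph is coherent: the drug is given every two weeks, so there is a next two-weekly dose to return to. For zimberelimab there is not. A site that misses a zimberelimab infusion is told to "follow the schedule for the next biweekly dose", and the next two-weekly visit is a Day 15 at which the drug is not scheduled. The minimum-interval sentence does not help, because 11 days is far below the four-week interval.

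Two sites could therefore handle the same missed infusion differently, each believing it had followed the protocol. What is at stake is the spacing of 480 mg infusions in individual patients, the count of missed doses, and whether a Day 15 infusion is recorded as compliant or as a deviation. SAP Section 6.3 lists dose errors with the investigational product among possible major deviations. SAP Section 1.1 says the abbreviated analysis will focus on safety, so dosing records matter to what will be reported.

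**Working it through.** **Inputs**
- SRF617 interval: 14 days (Protocol 7.1.2).
- Zimberelimab interval: 28 days (Protocol 4.4 and 7.3.1; SAP 2.2).
- Dosing window: 3 days either way (Protocol 7.1.3, under Table 5).
- Stated minimum for both drugs: 11 days (same paragraph).
- Planned zimberelimab dose intensity: 480 mg per cycle (SAP 8.1).

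**Step 1. Where the 11 days fits.** Take the interval less the window.
- SRF617: 14 − 3 = 11. This reproduces the stated figure.
- Zimberelimab: 28 − 3 = 25. It does not.
- Other constructions for zimberelimab also fail. Moving both doses by 3 days gives 28 − 6 = 22. Using Table 2's one-day visit window at both ends gives 28 − 2 = 26.

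The stated floor is 11/28 = 39% of the zimberelimab interval. These subtractions only test where the figure comes from; none is put forward as a rule.

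**Step 2. The literal reading, on the calendar.** Count Cycle 1 Day 1 as day 1. Cycle 2 Day 1 is then day 29, Cycle 2 Day 15 is day 43 and Cycle 3 Day 1 is day 57. Suppose the Cycle 2 Day 1 zimberelimab infusion is missed and given at the next two-weekly visit.
- First gap: 43 − 1 = 42 days.
- Second gap: 57 − 43 = 14 days. This passes the 11-day floor and is half the scheduled interval.
- Mean gap: (42 + 14)/2 = 28 days.
- Cumulative dose over three cycles: 3 × 480 = 1,440 mg, the same as planned.

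If the 3-day window were also used to shorten the second gap, it would be 14 − 3 = 11 days, exactly at the floor.

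**Step 3. The other reading.** The site skips the dose and resumes on the next Day 1. Infusions fall on days 1 and 57, with a gap of 56 days and 2 × 480 = 960 mg over the three cycles.

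**Step 4. What the SAP would show.** Relative dose intensity is cumulative dose divided by cycles initiated, as a percentage of the planned intensity. Assume three cycles count as initiated.
- Literal reading: 1,440/3 = 480 mg per cycle, and 480/480 = 100%.
- Skipping: 960/3 = 320 mg per cycle, and 320/480 = 66.7%.

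Both correctly record the drug given. What the SAP leaves open is whether the Day 15 infusion still leaves one missed dose at Cycle 2 Day 1, and whether it is a deviation.

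**Step 5. Whether another section settles it.** Section 7.3.2 refers back to Table 5 for timing. Section 7.4.1.2 limits zimberelimab holds to 56 days but gives no spacing on restart. Two-weekly zimberelimab appears only in background on other trials (Sections 1.6, 1.7 and 1.9). The paragraph under Table 5 is therefore the only missed-dose and minimum-interval text for zimberelimab in the two documents.

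**The case against.** The strongest defence is that the paragraph first says missed doses are not to be made up. Table 5, immediately above it, shows no zimberelimab on Day 15, and every schedule statement agrees. A sensible site would skip the infusion and resume at the next Day 1. This stands as a reasonable reading, and it rules out saying that the protocol directs sites to give zimberelimab on Day 15. It does not remove the problem: the same sentence goes on to refer both antibodies to a two-weekly dose that only one of them has.

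The second defence is that 11 days is a floor, which a 28-day schedule never breaches. This is also right. The floor does not contradict the schedule; it is simply too loose to protect it.

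A reader might go further and divide 28 by 11 to infer a dose rate about 2.5 times the plan. The documents do not support that. It would need infusions repeated every 11 days, which nothing in the protocol permits. On the literal reading, one short gap follows one long gap and the total dose is as planned. Nor is there support for saying that the exposure tables as a whole would be wrong: SAP Section 8.1 builds cumulative and planned doses from what is recorded, so a Day 15 infusion would be counted.

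Two further points limit the finding. The Pharmacy Manual, to which the paragraph refers sites, is not available here and may be clearer. And the sponsor has stopped enrollment, with 15 patients treated (SAP Sections 1.1 and 2), so the prospective benefit is small, although enrolled patients were allowed to continue treatment.

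**Conclusion.** The point holds as an internal inconsistency in an operative dosing instruction. The reference to a two-weekly dose conflicts with zimberelimab's stated schedule, and the 11-day minimum fits only SRF617. The realistic extent is one interval of 14 days instead of 28 after a missed infusion (11 if the window is also used), with no added cumulative dose, together with site-to-site differences in missed-dose counts and deviation classification.

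This rests on the literal reading being open to a site and on the Pharmacy Manual not resolving it. No safety harm is shown. Protocol Section 1.9 lists 480 mg only at four-week spacing, but that says nothing about the effect of a single shorter gap. Sample size, power and type I error do not depend on this point. Which missed-dose rule or interval is clinically right is not judged here.

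**What to change.** Reconcile the paragraph under Table 5 with the Synopsis dosing table, Sections 4.4 and 7.3.1, Table 2 and its footnote n, and SAP Sections 2.2 and 8.1. Zimberelimab should have its own missed-dose and minimum-interval statement, separate from SRF617's, with the content and value set by the clinical team. Check that the Pharmacy Manual agrees.

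Before database lock, list any zimberelimab infusion given off Day 1 (beyond the allowed window). Settle one convention for counting it and for deciding whether it is a deviation, and apply that convention across sites.

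The cost is one clarifying sentence and a short data check on 15 treated patients. No analysis method changes.

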#### 7.1.4. SRF617 Storage

SRF617 is supplied in vials for single use. Each vial contains 100 mg of SRF617 for IV infusion. The drug product vials should always be stored in the container provided to the pharmacy and should be stored at  $-20^{\circ}\text{C} \pm 5^{\circ}\text{C}$  (-13 °F to 5 °F) protected from light. Caution is required when handling SRF617. Pharmacists should follow standard procedures for handling investigational drugs, including avoidance of eye or skin contact with the drug product. If there is exposure to the drug product, the individual should treat for physical exposure (skin washing) or inhalation (move to fresh air, as necessary) and, if needed, seek medical advice. During the preparation of SRF617, drug product is diluted in normal saline (0.9% Sodium Chloride for Injection, United States Pharmacopeia) as diluent. Once diluted, SRF617 should be stored at  $2^{\circ}\text{C}$  to  $8^{\circ}\text{C}$  or at room temperature until infusion and administered within 4 hours.

#### 7.1.5. SRF617 Preinfusion Medications

For the first administration of SRF617 (C1D1), no preinfusion medication is required. If a Grade 1 or higher infusion-related AE is recorded at any dose, the following premedications should be administered for all subsequent doses for that patient:

- Antipyretics (oral acetaminophen 650-1000 mg)
- Antihistamine (oral or IV diphenhydramine 25-50 mg or equivalent)

Patients with a Grade 2 or higher infusion reaction should also be premedicated with a glucocorticoid (IV dexamethasone 20 mg or methylprednisolone 80 mg) for all subsequent infusions.

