### *Infusion-Related Reactions*

For infusion reactions of any grade/severity, immediately interrupt the SRF617 infusion and manage symptoms. Management of infusion reactions may require reduction in the rate of infusion or treatment discontinuation of SRF617, as outlined below:

- Grade 1 to 2 (mild or moderate): Once reaction symptoms resolve, resume the infusion at no more than half the rate at which the reaction occurred. If the patient does not experience any further reaction symptoms, infusion rate escalation may resume in increments and at intervals clinically appropriate up to the maximum rate of 100 mL/h.
- Grade 3 (severe): Once reaction symptoms resolve, consider restarting the infusion at no more than half the rate at which the reaction occurred. Repeat the procedure above in the event of recurrence of Grade 3 symptoms. Permanently discontinue SRF617 upon the third occurrence of a Grade 3 or greater infusion reaction.
- Grade 4 (life-threatening): Permanently discontinue SRF617 treatment.

No dose reductions of SRF617 for infusion-related reactions are recommended.

For any patient who has a Grade  $\geq 2$  infusion reaction with SRF617, steroid premedication should be used for all subsequent infusions (see Section [7.1.5](#)).

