|   | Grade 3
ALT/AST $> 5 \times$ ULN but $\leq 20 \times$ ULN | 
For suspected non-immune-mediated transaminase elevations:
 
 
Withhold etrumadenant and zimberelimab for up to 56 days.
 
Monitor LFTs at least weekly for a minimum of 4 weeks until transaminases return to <math>< 3 \times</math> ULN or Baseline.
 
Consider patient referral to GI specialist for evaluation and liver biopsy to establish etiology of hepatic injury.
 
If event resolves to Grade 1 or better within 56 days, resume etrumadenant with a one-level dose reduction (Table 9) and resume zimberelimab.a If not, permanently discontinue etrumadenant and zimberelimab and contact Medical Monitor.
 
 
For suspected immune-mediated transaminase elevations:
 
 
Permanently discontinue zimberelimab and contact Medical Monitor.
 
Withhold etrumadenant for up to 56 days.
 
Consider patient referral to GI specialist for evaluation and liver biopsy to establish etiology of hepatic injury.
 
Initiate treatment with corticosteroids equivalent to 1-2 mg/kg/day oral prednisone. If event does not improve within 48 hours after initiating corticosteroids, consider adding an immunosuppressive agent.
 
If event resolves to Grade 1 or better within 56 days, taper corticosteroids over <math>\geq 1</math> month and resume etrumadenant with a one-level dose reduction (Table 9).a If not, permanently discontinue etrumadenant and contact Medical Monitor.
 
 |  |
|   | Grade 4
ALT/AST $> 20 \times$ ULN                         | Permanently discontinue etrumadenant and contact Medical Monitor. For suspected immune-mediated transaminase elevations, follow Grade 3 management guidelines.   | Permanently discontinue zimberelimab and contact Medical Monitor. For suspected immune-mediated transaminase elevations, follow Grade 3 management guidelines.   |
|   | ALT/AST $> 3 \times$ ULN with                                       | 
 
Permanently discontinue etrumadenant and zimberelimab and contact Medical Monitor.
 
Monitor liver function at least weekly until values return to Baseline.
 
  |  |

| Event  | Severity                       | Etrumadenant action to be taken   | Zimberelimab action to be taken  |

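### Section 6.6.2 allows steroids for toxicity care or premedication only up to 10 mg/day with prior approval, while Section 7.1.5 and Table 10 direct much higher doses and nothing reconciles them

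*Protocol*

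**What the plan says.** **Protocol Section 6.6.2 (Prohibited Medications)** applies during the study treatment period.
- It bans a class: "Systemic immunosuppressive medications (eg, cyclophosphamide, azathioprine, methotrexate, thalidomide" and others, anti-TNF agents among them. For corticosteroids the ban is narrower: doses above 10 mg/day "prednisone or equivalent on a long-term basis are prohibited". Long-term is not defined.
- Its one systemic allowance for the uses at issue is acute and low-dose, at most 10 mg/day prednisone or equivalent: "systemic immunosuppressant medications for management of adverse events or premedication are allowed after Medical Monitor approval has been obtained".
- It states a consequence: "If there is a clinical indication for any medication or vaccination specifically prohibited during the trial, discontinuation from trial therapy may be required". Questions go to the Medical Monitor.

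**Protocol Section 7.1.5** says that patients with a Grade 2 or higher infusion reaction should also receive a glucocorticoid: "IV dexamethasone 20 mg or methylprednisolone 80 mg) for all subsequent infusions". The infusion-reaction text in Section 7.4.1.1 repeats that "steroid premedication should be used for all subsequent infusions", giving no dose of its own and referring back to 7.1.5.

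**Protocol Table 10** (Section 7.4.1.2) gives three instructions that matter here.
- Suspected immune-mediated hepatic Grade 3: "Initiate treatment with corticosteroids equivalent to 1-2 mg/kg/day oral prednisone". Then: "If event does not improve within 48 hours after initiating corticosteroids, consider adding an immunosuppressive agent". If the event resolves in time, one sentence sets a taper of at least a month and the resumption of etrumadenant.
- Gastrointestinal Grade 2, if recurrent or lasting more than 5 days: 1-2 mg/kg/day prednisone equivalent.
- Suspected immune-mediated gastrointestinal Grade 3: 1-2 mg/kg/day methylprednisolone, then oral prednisone. Etrumadenant may resume under the Grade 2 rule.

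The text after Table 6 also permits steroids for immune-related hematologic toxicity of Grade 3 or higher, with no dose.

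**The concern.** Section 6.6.2 names premedication and adverse-event management and caps both at 10 mg/day with prior approval. Those are the two uses for which Sections 7.1.5 and 7.4 direct more. Section 6.6.2 does not refer to either section, and no rule says which text prevails.

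A site that works from 6.6.2 could wait for approval or give a lower dose when treatment is urgent; the hepatic row sets its next step at 48 hours. A site that works from 7.1.5 or Table 10 could have that care recorded as prohibited medication, which SAP Section 6.3 lists among the deviations that may be assessed as major. For the further immunosuppressive agent, the 6.6.2 sentence on possible discontinuation can apply, while Table 10 plans to resume etrumadenant.

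**Working it through.** The plan has no figure of its own on this point. The check compares the directed doses with the 10 mg/day limit, and then asks whether 6.6.2 still applies when they are given.

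**1. Premedication (7.1.5).** The documents give no steroid conversion factors, so I use break-even values. The dose stays within 10 mg prednisone equivalent only if:
- 1 mg dexamethasone counts as at most 10/20 = 0.5 mg prednisone; or
- 1 mg methylprednisolone counts as at most 10/80 = 0.125 mg prednisone.

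Even milligram for milligram, 20 and 80 exceed 10.

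**2. Toxicity treatment (Table 10).** 1 mg/kg/day of prednisone exceeds 10 mg/day for any patient above 10 kg. At an assumed 70-90 kg:
- low end: 1 × 70 = 70 mg/day, and 70/10 = 7 times the limit;
- high end: 2 × 90 = 180 mg/day, and 180/10 = 18 times the limit.

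**3. Could this count as long-term?** For hepatic Grade 3, assume a linear 30-day taper to zero (the text says at least 1 month). Days above 10 mg/day during a taper from dose D are 30 × (1 − 10/D).
- D = 70: 30 × (1 − 10/70) = 25.7 days.
- D = 180: 30 × (1 − 10/180) = 28.3 days.
- Event resolving at once: 0 + 25.7 = about 26 days.
- Full dose up to the 56-day limit: 56 + 28.3 = about 84 days.

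Premedication recurs with each infusion, twice per cycle. Through Cycle 24 there are 2 × 24 = 48 infusions, so a reaction at the first leaves 48 − 1 = 47 premedicated infusions. The 84 days and the 47 infusions are ceilings under these assumptions (more infusions are possible past 2 years), not expected values.

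**4. Is the patient still in the study treatment period?**
- Premedication is given for an infusion of study drug, so yes.
- For gastrointestinal Grade 2, Table 10 lets etrumadenant continue at the same dose unless a modification is indicated, so steroid and study drug can overlap.
- For hepatic Grade 3 and gastrointestinal Grade 3, etrumadenant is withheld and may resume. Table 7 holds SRF617 for Grade 2-3 immune-mediated events and then resumes it. Protocol Section 4.7 ties the end-of-treatment visit to stopping the last study drug, so a hold does not end treatment. SAP Section 5.1 likewise ends the treatment period at that visit.

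**5. Does another clause rescue it?** Section 6.6.3 allows any other medication needed for the patient's welfare, but only if it is not expected to interfere with evaluating study drug. It does not name steroids or override 6.6.2.

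**The case against.** The best defence is that nothing here is forbidden outright. The corticosteroid ban reaches only long-term use above 10 mg/day, and one dose every two weeks or a short gastrointestinal course is not plainly long-term. On that view the 10 mg/day allowance governs discretionary use, while 7.1.5 and Table 10, being specific, govern the toxicities they name. Every clause then keeps a purpose. Section 6.6.2 also says only that discontinuation may be required, and it sends questions to the Medical Monitor.

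Much of this stands. A reader might infer that the protocol expressly bans the steroid doses it directs. It does not: the steroid conflict rests on the capped, approval-gated allowance. But the specific-over-general reading is one the site must supply, since no precedence rule is written and 6.6.2 names the same two uses. The defence also fails for the further immunosuppressive agent, because the long-term qualifier attaches to corticosteroids and not to the class.

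A second objection is that in hepatic Grade 3 zimberelimab is stopped and the other two drugs are held, so overlap with dosing arises only if etrumadenant resumes during the taper. That narrows the overlap with dosing but does not lift a rule that runs for the whole treatment period. That row also requires contact with the Medical Monitor when zimberelimab is stopped, which is not approval of the steroid.

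Third, the harm is inferred from the wording, with no observed case. That is correct and limits the weight of the point.

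**Conclusion.** The concern holds as an unreconciled conflict between Section 6.6.2 and Sections 7.1.5 and 7.4. The directed doses fall outside the only systemic allowance that 6.6.2 states for these uses, by a factor of 7 to 18 for Table 10 at an assumed 70-90 kg. For premedication they do so at any conversion above the break-even values. The further agent in hepatic Grade 3 falls within the class ban, though Table 10 only asks the site to consider it.

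Two further readings are tempting and unsupported. One is that a known number of patients were under-treated or recorded as deviations: the documents give no rate of Grade 2 or higher infusion reactions or of steroid-treated events, so the number among the 15 treated patients is unknown. The other is that results are distorted: no analysis set, efficacy estimate or safety estimate changes.

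The point concerns patient care and deviation classification, and is worth correcting because the care is time-sensitive and the correction is small. Although enrolment ended, SAP Section 2 says that patients already enrolled or consented could continue under the protocol, so the text still governed their treatment.

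**What to change.** Add to Section 6.6.2:

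> *Exception: glucocorticoid premedication per Section 7.1.5, and corticosteroids or other immunosuppressive agents used to manage toxicity per Section 7.4 (including Table 10 and the NCCN or institutional guidelines it cites), are permitted at the dose stated in those sections or, where none is stated, at the dose in the applicable guideline or per Investigator judgment. The 10 mg/day limit does not apply, treatment should not be delayed for prior Medical Monitor approval, and the Medical Monitor should be notified promptly.*

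The clause for unstated doses is needed because the further agent, the hematologic steroids and the guideline-based rows of Table 10 give none.

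The text cost is one short exception, carried in a protocol amendment. Data collection and analysis do not change. It does replace prior approval with prompt notification for these uses, a change in oversight that the sponsor should make knowingly.
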